## 1.0 TRIAL SUMMARY

Title	A Phase II Study of Pembrolizumab (MK-3475) in Hepatitis C Virus Positive and Negative Subjects with Advanced Hepatocellular Carcinoma who Progressed on or Were Intolerant to First-Line Systemic Therapy
Trial Phase	Phase II
Clinical Indication	Hepatocellular carcinoma (HCC)
Trial Type	Interventional
Product	Arm A: Pembrolizumab (MK-3475)  Arm B: Pembrolizumab (MK-3475) and Zepatier® (grazoprevir [MK-5172] and elbasvir [MK-8742]).
Type of control	No treatment control
Route of administration	Pembrolizumab: Intravenous  Zepatier: Oral
Trial Blinding	Unblinded Open-label
Eligibility	Male/female subjects with and without hepatitis C virus (HCV) genotype GT1 or GT4 with advanced HCC with no curative option will be enrolled in this trial.
Treatment Groups	There will be 2 treatment groups within this trial. The first treatment group Arm A will be pembrolizumab monotherapy at 200 mg every 3 weeks (Q3W). The second treatment group Arm B will be pembrolizumab at 200 mg Q3W plus Zepatier (grazoprevir 100 mg and elbasvir 50 mg) administered once daily (qday) for 12 to 16 weeks depending on the HCV GT as per the Zepatier label. Ribavirin (RBV) will be combined as per Zepatier label.
Number of trial subjects	Approximately 15 subjects will be enrolled per arm.
Estimated enrollment period	12-15 months
Estimated duration of trial	It is estimated that the trial will require approximately 18 months from the time the first subject signs the informed consent form (ICF) until the last subject's last study-related phone call or visit.

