# Proprietary Information of MD Anderson

Protocol # 2016-0251

Date: February 24, 2020

16

each subject will be followed for 30 days for AE monitoring. Serious AEs (SAEs) will be collected for 90 days after the end of treatment or 30 days after the end of treatment if the subject initiates new anticancer therapy, whichever is earlier. Virologic response will be collected for 12 and 24 weeks after the end of all HCV study therapy.

This study will be conducted in conformance with Good Clinical Practices (GCP).

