## 5.2 Trial Treatments

The treatment to be used in this trial are outlined in Table 3, Table 4, and Table 5. Please see prescribing information for Zepatier and RBV.

Table 3 Trial Treatments

Drug	Dose/Potency	Dose Frequency	Route of Administration	Regimen/Treatment Period	Use
Pembrolizumab	200 mg	Q3W	IV infusion	Day 1 of each 3-week cycle	Experimental
Zepatier	Tablet: 50 mg elbasvir and 100 mg grazoprevir	qday	PO	Daily See Table 4	Experimental
RBV	Capsule: 200 mg See Table 5	qday	PO	Daily	Experimental

Abbreviations: IV = intravenous; PO = oral; Q3W = every 3 weeks; qday = once daily; RBV = ribavirin.

The duration of Zepatier is dependent upon HCV GTs and presence or absence of resistance polymorphisms. Please see Table 4.

Table 4 Zepatier Trial Treatment Duration With or Without Cirrhosis

Patient Population	Treatment	Duration
GT1a: treatment-naïve without baseline NS5A polymorphisms 	Zepatier	12 weeks
GT1a: Treatment-naïve or PegIFN/RBV-experienced  or with baseline NS5A polymorphisms 	Zepatier + RBV 	16 weeks
GT1b: Treatment-naïve or PegIFN/RBV-experienced 	Zepatier	12 weeks
GT1a  or GT1b: PegIFN/RBV/PI-experienced 	Zepatier + RBV 	12 weeks
GT4: Treatment-Naïve	Zepatier	12 weeks
GT4: PegIFN/RBV-experienced 	Zepatier + RBV 	16 weeks

Abbreviations: GT = genotype; NS5A = non-structural protein 5A; PegIFN = pegylated interferon; RBV = ribavirin.

1. Patients who have failed treatment with PegIFN + RBV.
2. NS5A RAVs at amino acid positions 28, 30, 31, or 93. See Section 2.1 Testing prior to the initiation of therapy, subsection NS5A resistance testing in HCV GT1a-infected patients.
3. For patients with CrCl >50 mL per minute, the recommended dosage of RBV is weight-based (<66 kg = 800 mg per day, 66 to 80 kg = 1000 mg per day, 81 to 105 kg = 1200 mg per day, >105 kg = 1400 mg per day) administered in 2 divided doses with food. For patients with CrCl ≤50 mL per minute, including patients receiving hemodialysis, refer to the RBV tablet prescribing information for the correct RBV dosage.
4. The optimal Zepatier-based treatment regimen and duration of therapy for PegIFN/RBV/PI-experienced GT1a-infected patients with 1 or more baseline NS5A RAVs at positions 28, 30, 31, and 93 has not been established.
5. Patients who have failed treatment with PegIFN + RBV + HCV NS3/4A protease inhibitor (PI): boceprevir, simeprevir, or telaprevir.

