Urinalysis h	X e		X		X		X		X	X				
T3, FT4, and TSH h	X e		X	X	X		X		X	X		X		
AFP m	X e	X		X			X			X		X		
C-Reactive protein		X	X			X				X				
Fibrotest	X													
APRI	X													
Coagulation														
Serum IGF-1	X p			X			X			X				

Trial Period:	Screening Phase	Treatment Cycles (3-Week Cycles). 1 year or treatment or 17 cycles in total.									End of Treatment	Virologic Failure – Arm B s	Post-treatment		
		1	2	3	4	5	6	7	≥8	DC			Safety Follow-up l	Follow-Up Visits	Survival Follow-Up a
Treatment Cycle/Title:	Screening									DC					
Week (approximate)	0	3	6	9	12	15	18	21	24	At DC		30 days post last dose	Q9W post-DC	Q12W	
Scheduling Window (Days) b	-28 to -1	±3	±3	±3	±3	±3	±3	±3	±3	±3	±7	±7	±7	±7	
Child-Turcotte-Pugh (CTP) Calculation	X														
Viral testing															
HCV Ab	X														
HCV genotype Arm B	X														
HCV viral load q, r Arm B	X	X	X	X	X	X	X	X	X	X	X	X			
If (1) HBV+ or (2) anti-HBc+ and HBsAg- and viral load-negative:															
Anti-HBc (total and IgM), anti-HBs,	X														
HBsAg and HBV viral load m	X	X	X	X	X	X	X	X	X			X			
Anti-HBc (total), anti-HBe, anti-HBs, and HBeAg m	X				X				X			X			
Plasma for HCV viral resistance testing Arm B r	X	X r									X s				
CENTRAL Laboratory Assessments															
Blood for genetic analysis k		X													
Whole blood for biomarker studies (serum and plasma) k	X	X	X							X					
Whole blood for correlative studies (RNA and DNA) k	X	X	X							X					

Trial Period:	Screening Phase	Treatment Cycles (3-Week Cycles). 1 year or treatment or 17 cycles in total.								End of Treatment	Virologic Failure – Arm B s	Post-treatment		
		1	2	3	4	5	6	7	≥8			Safety Follow-up l	Follow-Up Visits	Survival Follow-Up a
Treatment Cycle/Title:	Screening	1	2	3	4	5	6	7	≥8	DC				
Week (approximate)	0	3	6	9	12	15	18	21	24	At DC		30 days post last dose	Q9W post-DC	Q12W
Scheduling Window (Days) b	-28 to -1	±3	±3	±3	±3	±3	±3	±3	±3	±3	±7	±7	±7	±7
Newly Obtained Tissue Collection k	X		X							X				
Efficacy Measurements														
Tumor imaging i	X j,n	X o		X		X				X		X	X	

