- k. **Blood samples** Blood collection will be performed at screening, pre-chemo at Week 3 (end of Cycle 1), Week 6 (end of Cycle 2), and at confirmation of progressive disease/end of treatment. Depending on response, 3 to 4 blood samples will be collected per subject. There will be up to a total of 120 blood samples (15 patients × 4 samples × 2 arms = 120 blood samples), which will be collected in 3 CPT- and 2 purple-top tubes. **Biopsies** will be required pre-treatment, after 6 weeks of Pembrolizumab therapy, and voluntarily upon progression. Biopsies will be taken 6 weeks after treatment has commenced with an optional biopsy upon progression. This sample should be drawn for planned analysis of the association between genetic variants in DNA and drug response. This sample will not be collected at that site if there is either a local law or regulation prohibiting collection, or if the IRB/ERC does not approve the collection of the sample for these purposes. If the sample is collected, leftover extracted DNA will be stored for future biomedical research if the subject signs the FBR consent. If the planned genetic analyses are not approved, but FBR is approved and consent is given, this sample will be collected for the purpose of FBR.
- l. SAEs will be followed through 90 days following cessation of treatment, or 30 days following cessation of treatment if the subject initiates new anticancer therapy, whichever is earlier.
- m. AFP and HBV viral loads (for subjects who were positive) will be measured. Anti-HBc antibody, HBV e antigen and Ab, and anti-HBs will be measured every 12 weeks (84±7 days) calculated from the date of allocation , or earlier if clinically indicated. HBV viral load and HbsAg are measured every 3 weeks.
- n. The following imaging studies are required at baseline: CT chest with or without contrast; MRI of abdomen and pelvis with or without contrast unless patient has contraindication for MRI or severely claustrophobic. After screening, triple-phase abdominal imaging and CT chest will be performed every 9 weeks until progression. .
- o. Every time imaging is done for re-staging
- p. If not previously determined. If previously determined a copy of the pathology report must be made available to MD Anderson
- q. HCV Serum RNA test at screening, every cycle for the first 8 cycles. This will give SVR4, SVR12 and SVR24 data and allow determination of kinetics of HCV serum RNA with pembrolizumab

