Trial Period:	Screening Phase	Treatment Cycles (3-Week Cycles). 1 year or treatment or 17 cycles in total.								End of Treatment	Virologic Failure – Arm B s	Post-treatment		
		1	2	3	4	5	6	7	≥8			Safety Follow-up l	Follow-Up Visits	Survival Follow-Up a
Treatment Cycle/Title:	Screening	1	2	3	4	5	6	7	≥8	DC		Safety Follow-up l	Follow-Up Visits	Survival Follow-Up a
Week (approximate)	0	3	6	9	12	15	18	21	24	At DC		30 days post last dose	Q9W post-DC	Q12W
Scheduling Window (Days) b	-28 to -1	±3	±3	±3	±3	±3	±3	±3	±3	±3	±7	±7	±7	±7

- r. Blood samples will be collected for HCV genotype and viral resistance mutation testing at baseline on day 1 prior to first dose. Blood might be collected if an increase in HCV viral load is detected for resistance genotype identification. This is stored in case of virologic failures and to characterize the resistance patterns of the subjects enrolled.
- s. Arm B. In subjects who achieve HCV RNA <LLOQ on therapy, who subsequently develop HCV RNA >LLOQ, the subject needs to return for viral assessment and determination of need to discontinue Zepatier.
- t. Arm B. Hepatic laboratory testing should be performed prior to therapy, at treatment week 8, and as clinically indicated. For patients receiving 16 weeks of therapy, additional hepatic laboratory testing should be performed at treatment week 12.
- u. After documented local site assessed disease progression, or the start of new anticancer treatment; contacts are approximately every 12 weeks by telephone. Updated survival status may be requested by the Sponsor at any time during the course of the study. Upon Sponsor notification, all subjects who do not/will not have a scheduled study visit or study contact during the Sponsor defined time period will be contacted for their survival status (excluding subjects that have a death event previously recorded).

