#### 3. Exploratory endpoints

The proportion of subjects achieving undetectable HCV RNA (TND) and HCV RNA <LLOQ (TD[u]) at Week 2, Week 4, and Week 12 or Week 16 (for those treated for 16 weeks), and the proportion of subjects achieving SVR4 in the immediate treatment arm.

- (1) **Objective:** To assess whether pembrolizumab in combination with Zepatier affects the course of viral infections in subjects with underlying HCV GT1 or GT4. We hypothesize that pembrolizumab in combination with Zepatier will help to reduce viral loads in those with untreated HCV..
- (2) **Objective:** To evaluate the response of HCV GT1 and GT4 to treatment as assessed by sustained virologic response at 4 and 12 weeks after the end of 12 to 16 weeks of pembrolizumab in combination with Zepatier dosing. Sustained virologic response is defined as HCV RNA below the LLOQ (either TD[u] or TND).
- (3) **Objective:** To evaluate the emergence of viral resistance-associated variants (RAVs) to pembrolizumab in combination with Zepatier in subjects with HCV GT1 or GT4 without RAVs as baseline ..
- (4) **Objective:** To evaluate the efficacy of pembrolizumab in combination with Zepatier as assessed by the proportion of subjects in the immediate treatment arm achieving

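### No HCV RNA draw in the flow chart is timed to SVR12 or SVR24, so Arm B subjects who stop pembrolizumab early have no sample for the primary endpoint

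*Combined protocol and SAP*

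**What the plan says.** - **Endpoint.** Sections 3.1, 8.4.1.1 and 8.13.1 make SVR12 a primary endpoint for Arm B. SVR24 is secondary (Section 3.2).
- **Promise.** Section 2.1 states "Virologic response will be collected for 12 and 24 weeks after the end of all HCV study therapy", and Section 1.0 says the same.
- **Schedule.** Section 7.1.4.2.1 takes the HCV RNA draw times from the Section 6.1 flow chart. Footnote q there reads "HCV Serum RNA test at screening, every cycle for the first 8 cycles. This will give SVR4, SVR12 and SVR24 data".
- **Grid.** The row for "HCV viral load" in Arm B has twelve marks: screening, cycles 1 to 7, '≥8', discontinuation, the virologic-failure visit, and the safety visit, which is set at "30 days post last dose". Nothing is marked under the 9-weekly follow-up visits or the 12-weekly survival contacts.
- **After progression.** Section 7.1.6.4.3 provides telephone contact only.
- **Anchor.** Section 3.1 counts SVR12 from the end of all HCV study therapy and, in the same sentence, from the end of all study therapy. Section 7.1.4.2.1.1 and the abbreviation list use only the second.
- **Timed exploratory endpoints.** Section 8.13.1 wants HCV RNA "at Week 2, Week 4, and Week 12 or Week 16 (for those treated for 16 weeks").

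**The concern.** SVR is timed from the last dose of the antiviral course, but every scheduled post-baseline HCV RNA draw hangs on the pembrolizumab calendar, apart from the visit triggered by virologic failure. A subject who leaves that calendar early is not sampled at the time that defines the primary endpoint. The reason is then cancer progression or toxicity, not virology.

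The SAP does not clearly absorb the gap. In Section 8.13.3 the intermittent rule needs a later observed value, which an early stopper lacks. The other two missing-data categories are written for premature discontinuation from the study. Section 5.6.2 (Discontinuation of Treatment) says that stopping treatment is not study withdrawal. A progressed subject in survival follow-up therefore falls between the rules, and whether that subject counts as a failure or leaves the denominator is open.

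**Working it through.** **Inputs.** Zepatier runs "for 12 to 16 weeks depending on the HCV GT as per the Zepatier label" (Section 1.0). Pembrolizumab is given on "Day 1 of each 3-week cycle" (Table 3). The safety visit is 30 days after the last dose, ±7 days (Section 6.1). Arm B has about 15 subjects. Assumptions: Zepatier starts on Cycle 1 Day 1, no cycle is delayed, last dose means last pembrolizumab dose, and the discontinuation draw is no later than the safety draw.

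**Formulas, in weeks from first dose.** Cycle k Day 1 = 3(k − 1). SVRx = regimen length + x. Safety visit = 3(k − 1) + 30/7, where k is the last cycle dosed; the window adds at most 1 week.

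**Footnote q on its own terms.** Cycle 8 Day 1 = 3 × 7 = week 21. The chart labels that column week 24 because it labels cycle 1 as week 3.

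| Regimen | SVR4 | SVR12 | SVR24 | Week 21 is | Week 24 is |
|---|---|---|---|---|---|
| 12 weeks | 16 | 24 | 36 | 9 weeks post-therapy | 12 weeks post-therapy |
| 16 weeks | 20 | 28 | 40 | 5 weeks post-therapy | 8 weeks post-therapy |

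The first eight cycles cover SVR4. They do not reach SVR12 at week 21 for either regimen; at week 24 they reach it for the 12-week regimen only. They never reach SVR24.

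**Full grid, including the safety visit.** Earliest last-dose cycle that gives a draw at or after the endpoint:
- SVR12, 12-week regimen: cycle 7 gives 18 + 4.3 = 22.3 (23.3 with the window), short of 24; cycle 8 gives 25.3. Threshold: cycle 8.
- SVR12, 16-week regimen: cycle 8 gives 25.3 (26.3), short of 28; cycle 9 gives 28.3. Threshold: cycle 9.
- SVR24, 12-week regimen: cycle 11 gives 34.3 (35.3), short of 36; cycle 12 gives 37.3. Threshold: cycle 12.
- SVR24, 16-week regimen: cycle 12 gives 37.3 (38.3), short of 40; cycle 13 gives 40.3. Threshold: cycle 13.

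A last pembrolizumab dose at weeks 6 to 15 puts the final draw at about weeks 10 to 19, at most about 7 weeks after a 12-week course. If last dose instead means the last Zepatier dose, the final draw is about 4 weeks after HCV therapy. On the anchor that includes pembrolizumab, the final draw at 30 days (37 with the window) is short of 84 days, so nobody has an SVR12 sample.

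**Size, as illustration only.** Section 4.3.1 cites a pembrolizumab study with 34 of 104 subjects in progressive disease: 34/104 = 0.327, and 0.327 × 15 = 4.9, about 5 subjects. If those five were counted as failures, SVR12 could not exceed 10/15 = 67% (90% CI 43% to 86%, Table 16) even with perfect virology, against the rates above 90% quoted in Section 4.2.1.3.

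The documents give no time on pembrolizumab for this population. Assuming it is exponential with a median of m months, the share still on drug at week 21 is exp(−ln 2 × 21/(4.345m)): 19%, 51% and 66% for m = 2, 5 and 8.

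**Timed exploratory endpoints.** Weeks 2, 4 and 16 are days 14, 28 and 112. The neighbouring cycle visits, with ±3 days, cover days 18–24, 39–45 and 102–108. None of the three endpoint days falls inside a window. Week 12 (day 84) coincides with Cycle 5 Day 1.

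**The case against.** The best defence is that the intended design already includes these samples. Sections 1.0 and 2.1 commit to them, and Section 7.1.4.2.1 speaks of draws after dosing. That is fair, and it makes this a conflict between text and schedule rather than a decision not to sample. It does not remove the problem, because Section 7.1.4.2.1 sends sites to the flow chart for the times and the flow chart has no such visit.

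A reader might infer more than the documents support:

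- **That SVR24 is unsampled for everyone, or SVR12 for every 16-week regimen.** This follows from footnote q alone, but the grid also marks '≥8', discontinuation and the safety visit. Treatment may run to 35 cycles (Section 7.1.6.3; the flow-chart heading says 17), so long-treated subjects do have draws at or after both times. If '≥8' means every later cycle, Cycle 13 Day 1 is exactly week 36. A long dose hold before discontinuation could also yield a late draw by chance.
- **That as many as 10 of 15 would be lost.** This comes from applying the 3.1-month median PFS in Section 4.2.1.1. That median belongs to regorafenib under modified RECIST. First progression also need not end cycle visits: Sections 2.1 and 7.1.4.1.5 let stable subjects continue until progression is confirmed 4 to 8 weeks later.
- **That unsampled subjects become failures.** Section 8.13.3 does not clearly say so for a subject still in the study.

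The 33% figure has limits too. It is a response category, with no date of progression or of stopping treatment.

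**Conclusion.** The point holds. No HCV RNA draw is timed to 12 or 24 weeks after HCV therapy, and footnote q's claim to deliver SVR12 and SVR24 fails on the plan's own calendar.

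On the full grid, SVR12 is lost for subjects whose last pembrolizumab dose is before about cycle 8 (12-week regimen) or cycle 9 (16-week regimen). SVR24 is available only incidentally, from about cycle 12 or 13. These thresholds rest on the timing assumptions listed above and on counting SVR from the end of HCV therapy. The figure of about 5 of 15 is an illustration; the defect does not depend on it.

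This must be fixed because it concerns a primary endpoint and a sample not drawn on time cannot be recovered. The mismatch at weeks 2, 4 and 16 is minor, since those endpoints are exploratory.

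**What to change.** 1. Add Arm B columns to the flow chart for HCV RNA at 4, 12 and 24 weeks after the last dose of HCV therapy, each with a window, for every Arm B subject whatever the pembrolizumab or progression status.
2. Correct footnote q so that it no longer claims SVR12 and SVR24 from the first eight cycles, and make it agree with the grid row.
3. State one SVR anchor. Reconcile Sections 3.1, 3.2, 7.1.4.2.1.1 and 8.13.1 and the abbreviation list on whether the clock starts at the end of HCV therapy or of all study therapy. The columns in item 1 assume the former.
4. Align the week 2, 4 and 16 endpoints with actual visits, either by adding draws or by restating them at weeks 3, 6 and 15. The flow chart already takes liver panels weekly in the first two cycles, so weeks 2 and 4 could share those draws.
5. Say in Section 8.13.3 how a subject who is still in the study but has no SVR12 sample is classified.

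Items 2, 3 and 5 are wording. Item 1 costs at most three draws per Arm B subject (3 × 15 = 45), of which the SVR12 and SVR24 draws are already promised. Some will need a clinic visit from subjects who would otherwise be followed by telephone.

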# Proprietary Information of MD Anderson

Protocol # 2016-0251

Date: February 24, 2020

13

	therapy, whichever is earlier. Virologic response (sustained virologic response [SVR]) will be collected for 12 and 24 weeks after the end of all HCV study therapy.
Estimated average length of treatment per subject	Subjects will be treated for up to 2 years or 35 cycles of pembrolizumab.

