### 3.1 Primary Objective(s)

- (1) **Objective: Arm A and Arm B:** To evaluate the tolerability of IV administration of pembrolizumab as second-line therapy in subjects with advanced HCC.
- (2) **Objective: Arm B:** To evaluate the efficacy of pembrolizumab in combination with Zepatier as assessed by the proportion of subjects with HCV GT1 or GT4 achieving Sustained Virologic Response 12 weeks after the end of all HCV study therapy (SVR12), defined as HCV RNA below the lower limit of quantitation (LLOQ) (either target detected unquantifiable [TD(u)] or target not detected [TND]) 12 weeks after the end of all study therapy.

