## 7.1.6.4 Post-Treatment Visits

### 7.1.6.4.1 Safety Follow-up Visits

The mandatory Safety Follow-up Visit should be conducted approximately 30 days after the last dose of trial treatment or before the initiation of a new anticancer treatment, whichever comes first.

All AEs that occur prior to the Safety Follow-Up Visit should be recorded. Subjects with an AE of Grade >1 will be followed until the resolution of the AE to Grade 0-1 or until the beginning of a new anticancer therapy, whichever occurs first. Serious AEs that occur within 90 days of the end of treatment or before initiation of a new anticancer treatment should also be followed and recorded.

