### 7.1.6.4.2 Follow-up visits

Subjects who discontinue trial treatment for a reason other than disease progression will move into the Follow-Up Phase and should be assessed approximately Q9W by radiologic imaging to monitor disease status. Every effort should be made to collect information regarding disease status until the start of new anti-cancer therapy, disease progression, death, or the end of trial, whichever occurs first. Information regarding post-trial anticancer treatment will be collected if new treatment is initiated.

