### 7.1.6.4.3 Survival Follow-up

Subjects who experience confirmed disease progression or start a new anticancer therapy, will move into the Survival Follow-Up Phase and should be contacted by telephone approximately Q12W to assess for survival status until death, withdrawal of consent, or the end of the trial, whichever occurs first.

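### The flow chart does not schedule the SVR12 and SVR24 samples that footnote q claims: an Arm B subject who stops pembrolizumab early has no charted HCV RNA draw for a primary endpoint

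*Combined protocol and SAP*

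**What the plan says.** Sections 3.1 and 8.4.1.1 make SVR12 a primary endpoint for Arm B. Section 1.0 promises the samples: "Virologic response (sustained virologic response [SVR]) will be collected for 12 and 24 weeks after the end of all HCV study therapy". Section 2.1 repeats this. Exploratory objective 9 in Section 4.1 and the HCV objectives in Section 8.13.1 name follow-up weeks 4, 12 and 24.

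The schedule itself is left to the flow chart. Sections 7.1.3.6 and 7.1.4.2.1 refer to Section 6.0 for the timing of HCV RNA draws. Section 5.6.2 refers to Sections 6 and 7.1.6.4 for what happens after treatment stops.

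In the chart, the Arm B HCV viral load row is marked at screening, cycles 1 to ≥8, discontinuation, virologic failure and the safety visit ("30 days post last dose"). It has no mark under Follow-Up Visits or Survival Follow-Up. Footnote q, attached to that row, says: "HCV Serum RNA test at screening, every cycle for the first 8 cycles. This will give SVR4, SVR12 and SVR24 data".

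The visit sections add no draw. The last visit with a charted routine draw is described in Section 7.1.6.4.1: "The mandatory Safety Follow-up Visit should be conducted approximately 30 days after the last dose of trial treatment". After a stop for reasons other than progression, subjects "should be assessed approximately Q9W by radiologic imaging to monitor disease status" (Section 7.1.6.4.2). After confirmed progression or new therapy they "will move into the Survival Follow-Up Phase and should be contacted by telephone approximately Q12W to assess for survival status" (Section 7.1.6.4.3).

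**The concern.** Footnote q presents sampling tied to pembrolizumab cycles as if it delivered endpoints that run on a different clock, the end of HCV therapy. The two clocks separate when a subject stops pembrolizumab early, which is foreseeable in second-line HCC. A site that follows the chart would then have no routine visit at which to take the SVR12 sample, and that sample cannot be recovered later. The rule in Section 8.13.3 for intermittent gaps would not help, because it needs a later observed value and no later draw is charted. With about 15 subjects in the arm, each lost result matters to the estimate.

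**Working it through.** **Inputs.** The Zepatier course is 12 or 16 weeks (Section 5.2, Table 4). Cycles last 21 days and the first dose is Cycle 1 Day 1 (Section 7.1.1.11). SVR12 and SVR24 fall 84 and 168 days after the last HCV dose. The safety visit is 30 days after the last dose, ±7 days (Section 6.1, Section 7.1.6.4.1). One assumption: Zepatier starts with the first pembrolizumab dose, called day 0. A later start would move the SVR dates later and widen the gaps.

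**1. What footnote q delivers.** Its last draw is Cycle 8 Day 1 = 7 × 21 = day 147, or week 21. The chart labels that column week 24, so both clocks are tried.

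**2. When the endpoints fall.**

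| Course | SVR12 due | SVR24 due | Shortfall from week 21 (SVR12, SVR24) | Shortfall from week 24 (SVR12, SVR24) |
|---|---|---|---|---|
| 12 weeks | 84 + 84 = day 168 (week 24) | 84 + 168 = day 252 (week 36) | 3 and 15 weeks | 0 and 12 weeks |
| 16 weeks | 112 + 84 = day 196 (week 28) | 112 + 168 = day 280 (week 40) | 7 and 19 weeks | 4 and 16 weeks |

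The footnote's claim is not reproduced for SVR24 on either clock or for either course, nor for SVR12 after a 16-week course. SVR12 after a 12-week course depends on which clock is used. SVR4 (week 16 or 20) lies within the eight cycles for a subject still being treated.

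**3. A subject who stops early.** Take a last pembrolizumab dose at Cycle 4 Day 1 = 3 × 21 = day 63, with the 12-week Zepatier course completed on day 84.

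- Safety draw counted from pembrolizumab: 63 + 30 = day 93. Shortfall to SVR12: 168 − 93 = 75 days.
- Safety draw counted from the last Zepatier dose: 84 + 30 = day 114. Shortfall: 168 − 114 = 54 days.
- With the full 7-day visit window the draws move to days 100 and 121, still 68 and 47 days short.
- On a 16-week course the corresponding shortfalls without the window are 196 − 93 = 103 days and 196 − (112 + 30) = 54 days.

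**4. What could fill the gap.** The Virologic Failure column is triggered by HCV RNA returning above the quantitation limit (footnote s), so it is not a scheduled SVR visit. The two later follow-up columns are empty for this row.

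**5. The other anchor.** Some definitions count SVR12 from the end of all study therapy. If that includes pembrolizumab, SVR12 is due 84 days after the last dose while the last charted draw is 30 days after it, a gap of 84 − 30 = 54 days. That reading does not close the gap.

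**The case against.** The best defence is that the text clearly requires these samples. Besides Sections 1.0 and 2.1, the objectives name the follow-up weeks, Section 7.1.4.2.2 has resistance blood taken during follow-up, and Sections 7.1.5.1 and 8.13.3 encourage subjects who stop treatment to stay in follow-up. The trial is single-site, and subjects who stop without progression still attend for imaging, so an off-chart draw is practical. This stands as far as it goes: the design intends the sample, and a careful site could obtain it. It does not repair the chart, to which the text assigns the timing.

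A second defence is the column headed ≥8. Read as every later cycle, it gives draws at week 24 (Cycle 9 Day 1) and week 36 (Cycle 13 Day 1), which match the 12-week course, and draws near the dates for the 16-week course. That may cover subjects still on pembrolizumab, although it contradicts the limit in footnote q. It does nothing for those who have stopped.

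Three stronger readings are tempting, and the documents do not support them.

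- **A firm dose cut-off, or the inference that every first-scan progressor is missed.** Section 5.2.1.2 allows dose holds: seven doses with one 3-week hold put the last dose at 126 + 21 = day 147 and the safety draw at day 177, after day 168. Repeated unconfirmed progression (Table 11, Section 12.2) can carry treatment to 70 + 56 + 56 = day 182. No SVR12 window is set, so near misses cannot be classified.
- **That progression also ends Zepatier.** Some general wording stops study treatment at progression, but Sections 2.1 and 5.2.1.6 direct that the antiviral course be completed or maintained.
- **That one missing result must read as 93% or 100% depending on the missing-data approach.** The contrast 14/15 against 14/14 requires tumour progression to count as unrelated to study drug. Section 8.13.3 also has a category for treatment-related stops, including for efficacy, which are failures under both approaches. Those categories concern leaving the study, which Section 5.6.2 distinguishes from stopping treatment.

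**Conclusion.** Footnote q is wrong as written for SVR24, and for SVR12 after 16-week courses. The chart and visit sections also provide no SVR12 draw for an Arm B subject who stops pembrolizumab well before the SVR12 date. In the day-63 example the last routine draw is 75 days early, or 54 days if counted from the last Zepatier dose.

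The number affected is not known. As an indication only, Section 4.3.1 cites a pembrolizumab HCC study in which 34 of 104 patients (33%) had progressive disease. The same share here would be about 5 of 15, and treatment beyond progression would lower it. The count could also be zero.

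A missing result scored as failure lowers the reported SVR12 rate by 1/15, or 6.7 points. How it would be scored is not settled by the text. No SVR12 threshold is set, so the exposure is to the estimate and not to a decision rule. Because off-chart sampling is possible, the conclusion is a risk to primary-endpoint data and not a certain loss.

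**What to change.** In Section 6.0, add HCV RNA draws 12 and 24 weeks after the last dose of HCV therapy for all Arm B subjects, whatever their progression or pembrolizumab status. Correct footnote q so that it no longer says the first eight cycles give SVR12 and SVR24. For full courses the draws fall at weeks 24 and 36, or weeks 28 and 40.

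The cost is one amendment and at most about 2 × 15 = 30 blood draws. Some subjects whose disease has progressed would have to return for up to two visits instead of having telephone contact only.
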